## Chapter 9: Statistical Considerations

## 9.1 Statistical and Analytical Plans

The approach to sample size and statistical analyses are summarized below.

## 9.2 Statistical Hypotheses

The primary outcomes for this study are CGM-measured percentage below 54 mg/dl and CGM-measured percent above 180 mg/dl over a 6-week period. The intervention will be considered effective if the 6-week follow-up % above 180 mg/dl value is superior and % below 54 mg/dl value is non-inferior to the corresponding baseline values using a statistical significance of  $\alpha=0.05$  and the analysis specified below in Section 6 (i.e.,  $p < 0.05$ ).

The null/alternative hypotheses are:

### Percentage below 54 mg/dl:

- a. *Null Hypothesis*: The difference in mean CGM-measured % below 54 mg/dl between the 6 weeks follow-up and baseline is greater than or equal to +1% (non-inferiority).
- b. *Alternative Hypothesis*: The difference in mean CGM-measured % below 54 mg/dl between the 6 weeks follow-up and baseline is less than +1%.

### Percentage above 180 mg/dl:

- a. *Null Hypothesis:* There is no difference in mean CGM-measured % above 180 mg/dL between the 6 weeks of follow-up and baseline (superiority).
- b. *Alternative Hypothesis:* The mean CGM-measured % above 180 mg/dL is different at baseline than the mean over 6 weeks of follow-up.

### 9.3 Sample Size

The planned cohort of N=30 participants with the goal of at least N=24 completing the study is a convenience sample not based on statistical principles.

## 9.4 Outcome Measures

#### 9.4.1 Primary Efficacy Endpoints

- CGM-measured percentage below 54 mg/dl
- CGM measured percentage above 180 mg/dl

#### 9.4.2 Secondary Efficacy Endpoints

- CGM-measured metrics:
  - Percentage in range 70-180 mg/dL
  - Percentage < 70 mg/dL
  - Percentage > 250 mg/dL
  - Percentage in tight glycemic range 70-140 mg/dL
  - Mean glucose

1172

1173       ➤ Up to 4hr post-prandial glycemic metrics:  
1174           ■ Peak  
1175           ■ Area Under the Curve (AUC)

1176

1177       • Insulin metrics  
1178           ➤ Total daily insulin use  
1179           ➤ Total basal insulin  
1180           ➤ Total bolus insulin  
1181       • Weight  
1182       • Questionnaires  
1183           ➤ Tandem Study-Specific Baseline Survey  
1184           ➤ Altarum Consumer Engagement Measure  
1185           ➤ Tandem Pump Training Survey  
1186           ➤ DAWN Impact of Diabetes Profile  
1187           ➤ Diabetes Impact and Device Satisfaction Scale  
1188           ➤ PROMIS Sleep-Related Impairment Questionnaire  
1189           ➤ System Usability Scale

1190

#### Calculation of CGM metrics

1191       • Baseline values will be taken from the last 7 days of the run-in, or for participants who  
1192       can skip the run-in baseline values will be taken from their personal CGM during the 7  
1193       days prior to initiating CLC. At least 24hr of data during this baseline period are required  
1194       for the glycemic metrics to be calculated.  
1195       • Follow-up values will be calculated using CGM data from the 6-week period of CLC use.  
1196       These will be limited to participants who have at least 168 hours of CGM data available  
1197       during the 6-week CLC use period.  
1198       • Exploratory analyses will include all CGM data between the initiation of Open-Loop use  
1199       and the start of CLC will be used. At least 24hr of data during this period are required for  
1200       the glycemic metrics to be calculated.  
1201       • Separate values for each CGM metric (except for post-prandial peak and 4-hour AUC)  
1202       will be calculated for:  
1203           ➤ Overall: 24 hours of the day  
1204           ➤ Daytime: CGM readings from 6:00 am – 11:59 pm  
1205           ➤ Nighttime: CGM readings from midnight – 5:59 am  
1206           ➤ During logged exercise challenges

1207

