
PARTICIPANT AREA	DESCRIPTION
Sample Size	Up to 30 individuals initiating use of the study system in closed-loop mode, with the goal of at least 24 completing the trial
Treatment Groups	All participants will use the study-assigned Control-IQ pump in closed-loop mode.
Participant Duration	~8-12 weeks, depending on duration of run-in phase
Study Duration (planned)	~5 months from first enrollment until last participant visit
Protocol Overview/Synopsis	
After consent is signed, eligibility will be assessed. Eligible participants not currently using a Dexcom G6 CGM or using a Dexcom G6 CGM with <85% of possible glucose values captured during the 14 days prior to enrollment will initiate a CGM run-in phase of 2-4 weeks. Participants who skip or successfully complete the CGM run-in will be trained on use of the study pump in open-loop mode and will initiate a pump run-in phase of 2-4 weeks that will include insulin therapy adjustment to optimize open-loop glycemic control.
 
Participants who successfully complete the open-loop pump run-in will be trained on use of the study pump in closed-loop mode and will use the study system (pump and CGM) in closed-loop mode for 6 weeks.
 
Subjects will be asked to use programmed sleep activity each night and perform exercise challenges with exercise mode enabled at least once per week.
 
Questionnaires will be given at the screening visit after consent; before starting closed-loop use (Control-IQ Phase); and after 6 weeks of closed-loop use. Semi-structured interviews will be performed at the end of the study to better determine the experience of using the study device
 
Study Safety Plan:
 
Participants will be given a blood glucose and ketone meter to use throughout the study, and will be trained on their use by qualified staff. BGM readings will be performed in accordance with the study safety plan and per CGM manufacturer instructions. Ketone readings will be performed per the study safety plan.
 
Site investigators may adjust insulin delivery profile settings as needed throughout the study in accordance with their clinical practice.

\* Current use of Dexcom G6 CGM with at least 85% of possible readings captured during the 14 days prior to enrollment

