168 to contribute ~10 participants (5 basal only / 5 MDI) toward the overall recruitment goal.

169 **2.1.1 Informed Consent and Authorization Procedures**

170 Potential eligibility may be assessed as part of a routine-care examination. Before completing  
171 any procedures or collecting any data that are not part of usual care, documented informed  
172 consent will be obtained.

173 Once a potential study participant has been identified, the study protocol will be discussed with  
174 the potential study participant by study staff. The potential study participant will be given the  
175 Informed Consent Form to read. Potential study participants will be encouraged to discuss the  
176 study with family members and their personal physicians(s) before deciding whether to  
177 participate in the study. If the potential study participant is interested in the study, the  
178 investigator will schedule a virtual or in-person visit to discuss study, and if the potential study  
179 participant agrees to participate, the Informed Consent Form will be electronically signed  
180 through the JCHR website. A copy of the electronically signed consent form can be printed by  
181 the participant and another copy will be printed by the site to add to the participant's study  
182 record. The site shall print a copy of the signed consent for the participant any time at the  
183 participant's request, at no cost, and without undue delay.

184 As part of the informed consent process, each participant will be asked to sign an authorization  
185 for release of personal information. This will be done electronically as part of the consent  
186 process. The investigator, or his or her designee, will review the study-specific information that  
187 will be collected and to whom that information will be disclosed. After speaking with the  
188 participant, questions will be answered about the details regarding authorization.

189 A participant is considered enrolled when the informed consent form has been electronically  
190 signed by both the participant and the investigator, and HIPAA authorization has been provided.

191 This process shall be document in the study records at each site (e.g., consent process note).

192 **2.2 Participant Inclusion Criteria**

193 Individuals must meet all of the following inclusion criteria in order to be eligible to participate  
194 in the study.

195 1. Age  $\geq$ 18 years old and residing in the US  

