## 295                   **Chapter 3: CGM and Pump Run-in Phases**

### 296                   **3.1 CGM Run-in Phase Overview**

297                   This phase must begin within 7 days of completion of the Screening visit. The purpose of this  
298                   CGM run-in phase is to 1) assess compliance with study procedures and 2) to introduce the study  
299                   CGM to study participants without current use of a Dexcom CGM.

300                   Participants who currently use a Dexcom G6 CGM with at least 85% of possible CGM readings  
301                   captured during the 14 days prior to enrollment can skip the CGM Run-in phase. Participants who  
302                   do not currently use a Dexcom G6 CGM, or who do use that CGM but have <85% of possible  
303                   CGM readings in the 14 days prior to the time of enrollment, will be required to participate in the  
304                   CGM Run-in phase.

305                   Participants will receive training on the study CGM as detailed below. This will be an unblinded  
306                   use of the study CGM.

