### 378 **3.6 Initiation of the Study Pump**

379 During an in-clinic visit, the study pump, associated supplies, and training will be provided to  
380 participants and the participant will be instructed to use the pump in open-loop mode in  
381 conjunction with the study CGM until the Pump Run-in review visit.

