## Chapter 4: Control-IQ (Closed-Loop) Phase

## 4.1 Control-IQ Phase Overview

478 Initiation of the Control-IQ study phase, involving use of the study pump in closed-loop mode for  
479 6 weeks, will coincide with the final Pump Run-in follow-up clinic visit described above.

480 During the Control-IQ phase, visits and contacts will be scheduled as outlined in Table 2 below:

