#### 4.3 Calculation of Overall CGM Metrics (primary and secondary):

- One Week of Baseline: The last 7 days of personal CGM data before enrollment or last 7 days of CGM run-in data will serve as baseline. If a participant has <24hr of data in the last 7 days of CGM personal or run-in and if more CGM data are available beyond the 7 days, then will go backwards 24hr at one time until the minimum of 24hr of CGM data are reached. At least 24hr of data during baseline are required for the glycemic metrics to be calculated. These are Dexcom sensor data.
- Six Weeks of CLC use: All CGM data following the midnight of the initiation of CLC use visit day and the midnight right before the end of study visit day will be included irrespective if the system was in closed-loop mode or not. Since the exercise sessions are designed as challenges to the system and the data to be analyzed for safety events, the CGM data between the start of the exercise and 6:00AM next morning will be analyzed separately (see Section 8.1 below) and not included here. On the other hand, since the meals are not designed to be challenges to the system, the CGM data following the meals will be included here even if also analyzed separately (see

Section 8.1 below). If the end of 6 weeks of CLC use visit is more than 6 weeks away from the CLC use initiation visit for a participant, then the CGM data will be truncated at 6 weeks (i.e., 42 days). At least 168hr of data during these 6 weeks of CLC use are required for the glycemic metrics to be calculated and for a participant to be included in the primary and secondary analyses. These are Tandem pump CGM data and will include data following meals and during exercise periods.

- Two-four Weeks of Open Loop (OL) use: All CGM data between the initiation of Open-Loop use and the start of CLC will be used. At least 24hr of data during this period are required for the glycemic metrics to be calculated. These are Tandem pump CGM data.
- All CGM metrics during baseline, OL, and CLC periods will be calculated giving equal weight to each sensor reading for each participant.

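### For participants who skip the CGM run-in, the protocol and the SAP take the baseline of both primary outcomes from different weeks that cannot overlap

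*Protocol*

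**What the plan says.** Protocol 9.4.2 (Calculation of CGM metrics) takes baseline from the last 7 days of the run-in. It makes an exception for participants who "can skip the run-in baseline values will be taken from their personal CGM during the 7", continuing on the next line "days prior to initiating CLC. At least 24hr of data during this baseline period are required".

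SAP 4.3 has a different rule: "The last 7 days of personal CGM data before enrollment or last 7 days of CGM run-in data will serve as baseline". If fewer than 24 hours of data fall in those 7 days, the SAP steps further back in time until 24 hours are reached.

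The surrounding sections fix where these weeks lie:

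- **Who skips, and what.** Protocol 3.1 says that current Dexcom G6 users with at least 85% of readings "captured during the 14 days prior to enrollment can skip the CGM Run-in phase". No provision lets anyone skip the pump run-in.
- **What comes before CLC.** The Protocol Summary describes a "pump run-in phase of 2-4 weeks that will include insulin therapy adjustment to optimize open-loop glycemic control". During it the study pump is worn in open loop in "conjunction with the study CGM until the Pump Run-in review visit" (Protocol 3.6).
- **When CLC starts.** Protocol 4.1 says that starting closed-loop use, planned for "6 weeks, will coincide with the final Pump Run-in follow-up clinic visit described above".
- **What enrollment means.** Protocol 2.1.1: "A participant is considered enrolled when the informed consent form has been electronically" signed by participant and investigator and the HIPAA authorization is in place.

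**The concern.** Both primary outcomes (% below 54 mg/dL and % above 180 mg/dL) are tested as paired differences between CLC and baseline. The baseline week therefore defines the effect being estimated.

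Under the protocol bullet, a skipper's change is CLC minus open-loop study-pump use after optimisation. If *the run-in* in that bullet means the CGM run-in, everyone else's change is CLC minus the therapy used before the study pump. One paired test would average these two contrasts. That is also not the comparison in SAP 6, which describes the comparator as a week of CGM use alone.

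No passage says which document takes precedence. Two live definitions of a primary baseline leave a choice that could be made after the data are seen. The stated purpose of the study is to inform the design of a larger one, and a mixed baseline would blur the estimate used for that.

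A lesser point is that the protocol asks for personal CGM data in a week when participants are told to wear the study CGM. Some skippers might lack 24 hours of such data. This is possible, not certain: the instruction to stop a personal CGM (Protocol 3.2) belongs to the run-in that skippers bypass.

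**Working it through.** The plan gives no figure to reproduce here; N=30 is a convenience sample. The check is interval arithmetic on the schedule for skippers, with day 0 = enrollment.

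**Inputs**

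| Step | Days | Source |
|---|---|---|
| Enrollment to screening visit | 0 to 28 | Protocol 2.4 |
| Screening to pump run-in start | 0 to 7 | Protocol 3.5 |
| Pump run-in | about 14 to 28 | Protocol Summary; 3.8 |
| CLC start | final pump run-in visit | Protocol 4.1 |

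**Formulas**

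- CLC day C = screening lag + lag to pump start + pump run-in length
- SAP window = days −7 to 0; protocol window = days C−7 to C
- Gap between the windows = C − 7; overlap = max(0, 7 − C)

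**Results**

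| Schedule | C | Protocol window | Gap | Overlap |
|---|---|---|---|---|
| Shortest: 0 + 0 + 14 | 14 | days 7 to 14 | 7 days | 0 |
| Longest permitted: 28 + 7 + 28 | 63 | days 56 to 63 | 56 days | 0 |

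All eight combinations of the minimum and maximum values give zero overlap. Overlap would need fewer than 7 days from enrollment to CLC, and the pump run-in alone takes about 14. The SAP look-back only moves its window earlier.

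For participants who do the CGM run-in, the pump run-in starts on the day of the final CGM run-in review (Protocol 3.5). Their SAP baseline therefore ends about 14 to 28 days before CLC.

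**Effect on the mean change.** The CLC value is the same under either rule, and only skippers' baselines differ. With the same participants analysed:

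difference in mean change = (share who skip) × (mean shift between skippers' two baseline weeks)

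Neither factor is in the documents, so all values below are assumptions.

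| Share | % >180, shift 5 points | % >180, shift 10 points |
|---|---|---|
| 10% | 0.10 × 5 = 0.5 | 0.10 × 10 = 1.0 |
| 25% | 0.25 × 5 = 1.25 | 0.25 × 10 = 2.5 |
| 50% | 0.50 × 5 = 2.5 | 0.50 × 10 = 5.0 |

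For % below 54 mg/dL, shifts of 0.1 to 0.5 points give 0.10 × 0.1 = 0.01 to 0.50 × 0.5 = 0.25 points, against a non-inferiority margin of +1 point.

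**The case against.** The strongest reply is that the intended baseline can be recovered from the documents. Protocol 9.1 says its chapter only summarises the approach, and the SAP gives the fuller rule. Protocol 9.16 treats open loop as a period additional to baseline, and another bullet in 9.4.2 makes it exploratory. On this view the protocol's anchor to CLC is a drafting slip. That is persuasive about intent and supports aligning to the SAP, but it does not remove the conflicting rule.

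The mixing of contrasts also depends on a reading. The Protocol Summary's Study Design row speaks of one initial run-in covering both CGM and open-loop pump use. If *the run-in* in 9.4.2 means that whole period, its last week is the week before CLC for everyone and no mixing occurs. This stands as a caveat. However, the protocol would then contradict the SAP for all participants, not only for skippers.

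The upper timing bounds are extremes. The Protocol Summary gives a participant duration of about 8–12 weeks. Less 6 weeks of CLC, that leaves 2–6 weeks (14–42 days) from enrollment to CLC, and so a gap of 7–35 days. The 63-day case implies 63 + 42 = 105 days, or 15 weeks. It is permitted by the visit windows but should not be expected. Non-overlap is unaffected.

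Finally, this is a pilot and the point shifts are illustrative. They cannot show that a conclusion would change, and the effect on % below 54 mg/dL looks small. The missing-data worry is weak too, because skippers already wear the same sensor model as the study CGM.

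**Conclusion.** The concern holds. For skippers, the two documents assign the baseline of both primary outcomes to different weeks, separated by about 7 to 56 days on the permitted schedule. One week is optimised open-loop use and the other precedes the study pump. This conclusion rests only on the documents' own timing rules.

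The numerical consequence is unknown. Under the assumed shares and shifts it is 0.5 to 5.0 points for % above 180 mg/dL and 0.01 to 0.25 points for % below 54 mg/dL, so the conflict matters mainly for the superiority outcome. Reading *the run-in* as the CGM run-in is the more natural choice, because nobody can skip the pump run-in, but the protocol does not say so. This should be fixed before analysis: the contradiction is certain, its size is uncertain, and the repair is cheap.

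**What to change.** Replace the baseline bullet in Protocol 9.4.2 with the SAP 4.3 rule: the last 7 days of the CGM run-in or, for participants who skip it, the last 7 days of personal CGM data before enrollment, with the same 24-hour look-back. Every baseline then precedes the study pump. Prior CSII or AID users, whom Protocol 2.2 admits, will still be on their own pump in that week.

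The cost is one bullet and no new data, since personal CGM downloads already reach back before screening (Protocol 1.4.1.10). A protocol amendment needs IRB approval (Protocol 11.2). If that is not wanted, a sentence in the SAP stating and explaining the departure from Protocol 9.4.2 would also settle which rule applies.

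The downside is that a skipper's baseline may end up to about 63 days before CLC, against about 14 to 28 days for the others, so skippers' change can span more calendar time. Tabulating the baseline-to-CLC gap would show this.

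Optionally, and not as correction of an error, state that the primary change covers the move to the study pump, optimisation and CLC together. A supportive paired CLC-minus-open-loop difference could then be reported with a 95% confidence interval and no p-value. The plan already describes the open-loop period alongside baseline and CLC, so this adds little work.

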#### **9.4.3 Safety Endpoints**

1208       • Severe hypoglycemia (needing assistance)  
1209       • DKA  
1210       • Hyperosmolar Hyperglycemic Syndrome  
1211       • Serious Adverse Events  
1212       • Unanticipated adverse device effects

1213

1215 **9.5 Analysis Datasets and Sensitivity Analyses**

1216 This is not a randomized trial so intent-to-treat does not apply. The primary analysis will be  
1217 limited to participants with at least 168 hours of CGM data during the 6-week CLC use period.

1218  
1219 A per-protocol analysis will be limited to participants who used the CLC for at least 80% of the  
1220 time during the 6-week period. If fewer than 10% of the study participants would be excluded  
1221 based on this criterion, then the per-protocol analysis will not be performed.

1222  
1223 Safety analyses will include all participants.

1224 **9.6 Analysis of the Primary Efficacy Endpoint(s)**

1225 Summary statistics appropriate to the distribution (e.g., mean and standard deviation, or median  
1226 and quartiles) will be for each of the primary efficacy endpoints (CGM-measured percentage  
1227 below 54 mg/dl and percentage above 180 mg/dl) at baseline, during CLC use, and for the  
1228 change values. Scatterplots and boxplots will be constructed to show the distribution of values at  
1229 baseline and during CLC use.

1230

1231 A pre- and post-CLC comparison will be performed using a paired t-test for each metric. If the  
1232 paired differences (i.e., change values) do not follow an approximate normal distribution, then a  
1233 non-parametric comparison based on ranks will be performed.

1234

1235 **9.7 Analysis of the Secondary Endpoint**

1236 Analysis of secondary endpoints will parallel the analysis described above for the primary  
1237 endpoints over 24 hours, daytime, and nighttime. For the post-prandial CGM metrics (4 hour  
1238 peak and AUC) and during exercise challenges, there will be no corresponding pre-study  
1239 baseline. Descriptive analyses of these metrics will be limited to values during CLC use.

1240 **9.8 Safety Analyses**

1241 All participants will be included in the safety analyses. All adverse events will be tabulated with  
1242 separate lists for events that occur before, during OL, and during CLC use.

1243  
1244 Additionally, the number of events and the event rate per 100 person-years during CLC use will  
1245 be calculated for each of the safety outcomes listed above:

- 1246 • Severe hypoglycemia (needing assistance)
- 1247 • DKA
- 1248 • Hyperosmolar Hyperglycemic Syndrome
- 1249 • All Serious Adverse Events
- 1250 • Unanticipated adverse device effects

1252                   **9.9 Intervention Adherence**

1253 Descriptive summary statistics will be given for the percentage of time that the CLC is in active  
1254 mode and the amount of CGM use over the 6-week period. A scatterplot of these two  
1255 percentages will be constructed. Boxplots will be given for each of these percentages for each of  
1256 the 6 weeks of follow-up. Descriptive statistics will be given for the percentage of time spent in  
1257 each of the CLC operational modes.

1258                   **9.10 Protocol Adherence and Retention**

1259 The following measures of adherence will be tabulated during the 6-week follow-up period:

- 1260     • Number of protocol and procedural deviations
- 1261     • Flow chart accounting for all enrolled participants up to the end of study
- 1262     • Flow chart of all enrolled participants at all scheduled visits and phone contacts post  
1263        treatment initiation
- 1264     • Number of and reasons for unscheduled visits and phone calls
- 1265     • Number of participants who stopped OL or CLC use and reasons

1267                   **9.11 Baseline Descriptive Statistics**

1268 Baseline demographic and clinical characteristics of the cohort of all enrolled participants will be  
1269 summarized in a table using summary statistics appropriate to the distribution of each variable.  
1270 Descriptive statistics will be displayed for the following:

- 1271     • Age
- 1272     • Sex
- 1273     • Race/Ethnicity
- 1274     • Diabetes duration
- 1275     • Insulin method before enrollment (basal only or multiple daily injections)
- 1276     • CGM use before enrollment
- 1277     • HbA1c
- 1278     • BMI
- 1279     • Participant-reported number of SH and DKA 12 months prior to the start of the study
- 1280     • Baseline CGM metrics including:
  - 1281        • % time < 54 mg/dl
  - 1282        • % time > 180 mg/dl
  - 1283        • % in range 70-180 mg/dl
  - 1284        • mean glucose
  - 1285        • % time < 70 mg/dl

1286

1287                   **9.12 Device Issues**

1288 The following tabulations and analyses will be performed to assess device issues:

- 1289     • Device malfunctions requiring study team contact and other reported device issues

1290 • Rate of different failure events and alarms per 24 hours recorded by the Control-IQ system –  
1291 overall and by study week

1292 **9.13 Planned Interim Analyses**

1293 No formal interim efficacy analyses are planned.

1294 **9.14 Sub-Group Analyses**

1295 In exploratory analyses, the primary outcomes (percent <54 mg/dl and percent >180 mg/dl) will  
1296 be compared in baseline subgroups. A least squares regression will be fit with the dependent  
1297 variable being the paired difference (value during CLC use minus value at baseline) and the  
1298 subgroup factor as an independent variable.

1299 Interpretation of subgroup analyses will be viewed with caution, particularly in the absence of an  
1300 overall significant difference. Subgroups will be analyzed according to the following baseline  
1301 factors:

1302 • Gender  
1303 • Race/Ethnicity (if sufficient numbers in more than one category)  
1304 • Insulin  
1305 ➤ Basal only (Group A)  
1306 ➤ Multiple daily injections (Group B)

1307 **9.15 Multiple Comparison/Multiplicity**

1308 There will be no formal correction for multiple comparisons in this pilot study.

1309 **9.16 Exploratory Analyses**

1310 The primary analysis described above in Section 9.6 will be repeated with the CGM-measured  
1311 percentage below 54 mg/dl and percentage above 180 mg/dl during follow-up limited to times  
1312 when the CLC was in active mode.

1313 Weekly boxplots for selected glycemic and insulin metrics will be generated.

1314 In addition to the baseline and 6 weeks CLC use period, the glycemic and insulin analyses will  
1315 be extended to include the 2-4 weeks of OL use. Only descriptive summary statistics and plots  
1316 will be generated for these new analyses.

